**Ad26.RSV.preF Clinical Data**

Ad26.RSV.preF is currently under evaluation in three other ongoing clinical studies: Phase 1 study (VAC18193RSV1003), and two Phase 2a studies (VAC18193RSV2002 and VAC18193RSV2003) (Table 4).

**Table 4: Other Ongoing Clinical Studies with Ad26.RSV.preF**

Study Identifier	Clinical Phase	Vaccine	N Planned	Study Population
VAC18193RSV1003	1	Ad26.RSV.preF	72	Adult subjects aged 60 years and older
VAC18193RSV2002	2a	Ad26.RSV.preF	44-70	Adult subjects aged 18 to 50 years
VAC18193RSV2003	2a	Ad26.RSV.preF	180	Adult subjects aged 60 years and older

In one of these studies, interim safety and immunogenicity data are available, as follows:

VAC18193RSV1003: This is an ongoing single-center, randomized, placebo-controlled, double-blind, FIH, Phase 1 study to evaluate the safety, tolerability and immunogenicity of 2 Ad26.RSV.preF vaccinations, administered 1 year apart, in 72 male and female subjects aged 60 years and older in stable health. Subjects have been randomized in parallel to one of five study groups and have received two intramuscular injections as follows:

- Group 1 –  $5 \times 10^{10}$  vp Ad26.RSV.preF on Day 1 and 1 year later;
- Group 2 –  $5 \times 10^{10}$  vp Ad26.RSV.preF on Day 1 and placebo 1 year later;
- Group 3 –  $1 \times 10^{11}$  vp Ad26.RSV.preF on Day 1 and 1 year later;
- Group 4 –  $1 \times 10^{11}$  vp Ad26.RSV.preF on Day 1 and placebo 1 year later;
- Group 5 – placebo on Day 1 and 1 year later.

Safety and immunogenicity data from the unblinded (at the study group level) analysis 28 days post-dose 1 from all 72 subjects who received Ad26.RSV.preF ( $5 \times 10^{10}$  vp or  $1 \times 10^{11}$  vp) or placebo confirmed that the  $1 \times 10^{11}$  vp dose of Ad26.RSV.preF was more immunogenic compared with the  $5 \times 10^{10}$  vp dose. Data from this ongoing study, which is still blinded, show that the Ad26.RSV.preF vaccine is immunogenic and that there is a favorable Th1/Th2 profile. No safety concerns were revealed; the reactogenicity of both doses was comparable.

For Study VAC18193RSV1003, Ad26.RSV.preF was provided in a different buffer (Formulation Buffer 1a) from the one to be used in the current study (Formulation Buffer 2b). The formulation buffer was changed to enhance the Ad26.RSV.preF drug product stability at 2 to 8 °C for storage purposes in future studies. The new formulation buffer was considered well-

tolerated when tested in a nonclinical single-dose intramuscular safety study in rabbits, and will be assessed in Cohort 0 before commencement of dosing Cohort 1 in the current study.

### **Safety Data Supporting Dose Selection from Other Ad26-based Vaccines**

In addition to the two completed studies with Ad26.RSV.FA2 and one ongoing study with Ad26.RSV.preF, the dose levels for Ad26.RSV.preF used in this study are supported by experience in adults with other Ad26 vaccines encoding for different antigens (EnvA [in Ad26.ENVA.01 against HIV]; CS protein [in Ad26.CS.01 against malaria]; and Ebola glycoprotein [in Ad26.ZEBOV against Ebola virus]). Note that, in general, at a given dose level, no significant changes in the safety profiles of Ad26-based vaccines have been seen when the transgene has been changed.

In completed clinical studies,a the safety of Ad26.ENVA.01, Ad26.CS.01 and Ad26.RSV.FA2 has previously been evaluated in at least 293 adult subjects, of whom 243 have received  $5 \times 10^{10}$  vp, and found to be well-tolerated. In addition, four Phase 1 studies with Ad26.ZEBOV have been completed in adults: 291 subjects have received Ad26.ZEBOV at  $5 \times 10^{10}$  vp and  $1 \times 10^{11}$  vp without significant safety issues: 15 subjects have received  $1 \times 10^{11}$  vp (25 doses administered), and 276 subjects have received  $5 \times 10^{10}$  vp. The safety data from these Ebola studies showed no safety concerns at  $5 \times 10^{10}$  vp and  $1 \times 10^{11}$  vp. Overall, these clinical data are supportive of dosing Ad26.RSV.preF at  $5 \times 10^{10}$  vp and  $1 \times 10^{11}$  vp in the current study.

To date, Ad26-vectored vaccines have only been tested in adults and the elderly (ie, subjects  $\geq 18$  years); Ad35-vectored vaccines have been tested in 904 subjects, including 555 adults and 349 infants. Data from Bacillus Calmette-Guérin (BCG)-primed infants immunized with Ad35 encoding for TB antigens (AERAS-402) indicated that the highest immune responses were obtained following administration of  $1 \times 10^{11}$  vp. The safety of this Ad35-based TB vaccine was acceptable when tested in infants aged 14 weeks and older at doses from  $1.5 \times 10^8$  vp to  $1 \times 10^{11}$  vp.

### **Study Design**

In the current study, homologous regimens will be evaluated in subjects in two sequential cohorts.

- In 18 to 50 year-old adults (Cohort 0):  
 $1 \times 10^{11}$  vp Ad26.RSV.preF (or placebo) on Days 1 and 29
- In 12 to 24 month-old RSV-seropositive toddlers (Cohort 1):  
 $5 \times 10^{10}$  vp Ad26.RSV.preF (or placebo) on Days 1 and 29

---

a Safety data from these studies are summarized in a separate report (Adenoviral Vaccine Safety Database V2.0, December 2016) which is available on request.

A dose of  $1 \times 10^{11}$  vp will be used for adults in Cohort 0 based on an acceptable safety profile of Ad26.RSV.preF at  $1 \times 10^{11}$  vp from the unblinded (at the group level) interim analysis 28 days post-Dose 1 from all 72 elderly subjects in study VAC18193RSV1003, in addition to supporting safety data from dosing Ad26.ZEBOV at  $1 \times 10^{11}$  vp.

A dose of  $5 \times 10^{10}$  vp will be used for toddlers in Cohort 1 as this is the anticipated dose to be used in a future study in 12-24 month-old seronegative toddlers. Dosing ranging would occur in a future study in 6 to 12 month-old seronegative subjects.

Enrollment and dosing will be staggered to allow safety assessments to be made in adults before enrolling and dosing seropositive toddlers, as described fully in Section 3.1 below.

An independent data monitoring committee (IDMC) will be established for this study to evaluate safety and tolerability data on a regular basis. Refer to Section 11.9.1, for details.

An independent blinded clinical endpoint committee (CEC) will be established for this study to assess any suspected case of severe lower LRTI in pediatric subjects. Refer to Section 11.9.2, for details.

## **1.2. Overall Rationale for the Study**

This study seeks to evaluate the safety and immunogenicity of Ad26.RSV.preF at a dose of  $5 \times 10^{10}$  vp in RSV-seropositive toddlers aged 12 to 24 months (Cohort 1). As this is the first study using Ad26.RSV.preF in Formulation Buffer 2, the reactogenicity profile of Ad26.RSV.preF in this new formulation buffer will be first assessed in an adult run-in cohort (Cohort 0) before dosing the toddlers.

## **2. OBJECTIVES, ENDPOINTS, AND HYPOTHESIS**

### **2.1. Objectives and Endpoints**

#### **2.1.1. Objectives**

##### **Primary Objectives**

The primary objectives are:

- To assess the safety and tolerability of an intramuscular regimen of two doses of  $1 \times 10^{11}$  vp of Ad26.RSV.preF in adults aged 18 to 50 years.
- To assess the safety and tolerability of an intramuscular regimen of two doses of  $5 \times 10^{10}$  vp of Ad26.RSV.preF in RSV-seropositive toddlers aged 12 to 24 months.

##### **Secondary Objective**

The secondary objective is:

- To assess the humoral and cellular immune responses as measured by virus neutralization assay, F-protein binding antibodies (pre-F and post-F) and intracellular cytokine staining (ICS; to assess Th1/Th2 subtyping).

### **Exploratory Objectives**

The exploratory objectives are:

- To further assess the humoral and cellular immune responses elicited by Ad26.RSV.preF. The assays to be used may include, but are not limited to, RSV strain cross-neutralization, anti-F protein antibody specificity and functionality characterization, adenovirus neutralization assays, molecular antibody characterization (avidity, Fc cell interaction, antibody isotyping), evaluation of the cellular immune response (IFN $\gamma$  enzyme-linked immunospot [ELISpot] assay) and functional and memory immune response (by ICS), and cytokine profiles of RSV F-protein peptide-stimulated peripheral blood mononuclear cell (PBMC) supernatant.
- To assess RSV infection rates in Ad26.RSV.preF and placebo subjects
- To monitor for severe RSV-LRTI in Cohort 1 (RSV-seropositive toddlers aged 12 to 24 months)
- To assess symptoms of respiratory illness via the respiratory tract infection (RTI) symptoms form

### **2.1.2. Endpoints**

#### **Primary Endpoints – Safety and Tolerability**

- Solicited local and systemic AEs for 7 days after each vaccination.
- Unsolicited AEs for 28 days after each vaccination (ie, from informed consent form [ICF] signature through the following 28 days post-first vaccination, and for subsequent vaccinations from time of vaccination through the following 28 days).
- SAEs from ICF signature to the end of the study.

#### **Secondary Endpoints – Immune Responses**

The analysis of the immunogenicity of vaccine regimens will include the characterization of humoral as well as cellular responses. The focus of the immunogenicity analysis is on virus neutralizing antibodies (VNAs), F-protein antibodies (pre-F and/or post-F) and Th1/Th2 cytokine profile response.

#### ***Humoral Immune Response***

- RSV neutralization A strain  
Analysis of RSV A neutralizing antibodies.

- RSV F-protein enzyme-linked immunosorbent assay (ELISA; pre- and/or post-fusion F antibodies)

Analysis of antibodies binding to RSV F protein in post-fusion and pre-fusion form.

### ***Cell-mediated Immune Response***

- Intracellular cytokine staining or cytokine analysis\*

Analysis of CD4 and CD8 T-cell subsets and their cytokine expression patterns will be determined by flow cytometry after RSV F-protein peptide stimulation (including, but not limited to CD4/CD8, interleukin-2 [IL-2], IFN $\gamma$ , TNF $\alpha$  and Th1/Th2 subtyping).

*\*Cytokine analysis for Th1/Th2 profiling will be done in cases where no ICS data can be generated due to insufficient number of PBMCs for ICS assay (see exploratory endpoints below for description)*

### **Exploratory Endpoints – Immune Responses**

Additional exploratory analyses may be performed to investigate vaccine-elicited immune responses further. These may include, but are not limited to, the following assays:

#### ***Humoral Immune Response***

- RSV cross-neutralization of B and/or other A strain(s)

The strain cross-neutralizing capacity of the vaccine-induced immune response will be assessed.

- F-protein antibody specificity characterization

Pre- and post-F specificity by binding or functional assays as ELISA, and/or competition ELISA. Adsorption of serum or plasma with pre-F and post-F protein before any antibody assay, epitope mapping, functional VNAs.

- Adenovirus neutralization assay

This assay assesses neutralizing antibody responses against the adenoviral vector.

- Functional and molecular antibody characterization

Functional characterization of antibodies may be performed in assays including antibody-dependent cell-mediated cytotoxicity (ADCC) and antibody-dependent cellular phagocytosis (ADCP). A molecular characterization of vaccine-elicited antibodies will include antibody avidity, Fc characterization and Ig isotype, functional VNA and protective antibody assessments.

#### ***Cell-mediated Immune Response***

- IFN $\gamma$  ELISpot assay

An ELISpot assay is used to quantify the amount of PBMCs able to produce IFN $\gamma$  upon RSV F-protein peptide antigen stimulation.

- Cytokine analysis

Cytokine profiles of (in vitro) stimulated PBMC supernatant will be analyzed to assess the quantity and quality of the elicited immune responses, including Th1/Th2 balance. Analysis will include, but is not limited to, IFN $\gamma$ , IL-2, IL-4, IL-5, IL-13, and TNF $\alpha$ .

### Exploratory Endpoints – RSV Infection

- For Cohort 1 only, RSV infection confirmed by either reverse transcriptase polymerase chain reaction (RT-PCR), or by serology for, but not limited to, protein G and/or N if no RT-PCR is available. To detect asymptomatic RSV infections, a fold increase will be applied to call a subject seropositive to G and/or N ELISA (or F in case of placebo subjects). Fold increases for RSV infection will be determined based on the (suspected) infection and the convalescent blood samples.
- In Cohort 1 throughout the study:
  - Severe RSV-LRTI
  - RSV medically-attended respiratory tract infection (MA-RTI)

Refer to Section 9.2 for evaluations related to endpoints.

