### **Exploratory Endpoints – RSV Infection**

- For Cohort 1 only, RSV infection confirmed by either reverse transcriptase polymerase chain reaction (RT-PCR), or by serology for, but not limited to, protein G and/or N if no RT-PCR is available. To detect asymptomatic RSV infections, a fold increase will be applied to call a subject

seropositive to G and/or N ELISA (or F in case of placebo subjects). Fold increases for RSV infection will be determined based on the (suspected) infection and the convalescent blood samples.

- In Cohort 1 throughout the study:
  - Severe RSV-LRTI: for subjects in Cohort 1, severe RSV-LRTI will be defined as the presence of severe LRTI as assessed by the clinical endpoint committee (CEC), and a positive assessment for RSV.
  - RSV medically-attended respiratory tract infection (MA-RTI): all subjects with RSV-RTI that is medically attended, ie, when the subject's parent/legal guardian seeks medical attention outside of normal study procedures, including health care professional's visit to the home, clinic visit, emergency room attendance, and hospital admission. (*Note*: medical attention outside normal study procedures will as much as possible also be captured on the RSV Symptoms Form.)

Note: Data on these 2 exploratory endpoints will be collected to assess the feasibility of, and gain expertise in the collection of such events for future studies.

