## 1. INTRODUCTION

A human adenovirus-vectored vaccine candidate which has shown promise in preclinical animal models of respiratory syncytial virus (RSV) will be assessed in this study:

Ad26.RSV.preF (JNJ-64400141), a replication-incompetent adenovirus serotype 26 (Ad26) containing a deoxyribonucleic acid (DNA) transgene that encodes for the pre-fusion conformation-stabilized F protein (pre-F) derived from the RSV A2 strain.

For the most comprehensive nonclinical and clinical information regarding Ad26.RSV.preF, refer to the latest version of the Investigator's Brochure for Ad26.RSV.preF.

The term "sponsor" used throughout this document refers to the entities listed in the Contact Information page(s), which will be provided as a separate document.

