Outside of the RSV season, nasal turbinate samples will only be collected from subjects with MA-RTIs or severe LRTIs (for definition of MA-RTI and severe LRTI, please refer to Section 11.3.1).

Throughout the study, nasal turbinate samples will be collected from any subject with a MA-RTI or severe LRTI.

The criteria used to assess potential cases of RSV infection in subjects from Cohort 1 will be as follows:

- Suspected RSV infection: subject has persistent (>48 hours) clinical symptoms of rhinitis (sneezing or runny nose or congestion) and persistence (>24 hours) of one or more of the following: cough, abnormal breathing, fever, lethargy or decreased appetite.

Occurrence of this combination of symptoms in any subject would trigger collection of a nasal turbinate sample.

---

a These procedures should preferentially be performed at the study site. These procedures can be conducted at the subject's home by site staff or qualified professional staff if the study site has an established standard operating procedure as such. In case of emergency, the procedures can be done in a hospital.

- Confirmed RSV infection: subject with suspected RSV infection and positive for RSV on the basis of RT-PCR conducted centrally.

Data on the clinical course of infection including information regarding oxygenation status, supplemental oxygen requirements and specific drug treatments should be collected, as well as any other concurrent respiratory illness present at the time of the diagnosis of the event and up to symptom resolution.

To ensure the rapid follow-up of any severe LRTI or MA-RTI, study sites will need to make arrangements with primary care physicians, emergency departments and/or hospitals' urgent care facilities to be notified when a subject is being seen. Further details will be provided in the Trial Center File. Any parent/legal guardian who seeks medical attention for their child due to an RTI should make the attending health care professional aware that their child is taking part in an RSV vaccine study. Each child's parent/legal guardian will be given a wallet card with key study information and site contact details (see Section 12.3.1). These details should be shared with the attending health care professional.

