#### **11.6. RSV Infection**

Incidence of any RSV infection, as described in Section 3.2, in Ad26.RSV.preF and placebo subjects will be summarized by descriptive statistics.

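### SAP 7 summarises RSV infection only if a severe LRTI occurs, and no by-arm analysis covers the serological part of the endpoint

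*Protocol*

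**What the plan says.** **Objective.** Protocol 2.1.1 lists as exploratory "To assess RSV infection rates in Ad26.RSV.preF and placebo subjects". SAP 1.1 repeats it. Neither attaches a condition.

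**Endpoint.** The Synopsis and Protocol 2.1.2 define Cohort 1 RSV infection by RT-PCR, "or by serology for, but not limited to, protein G and/or N if no RT-PCR is available". For asymptomatic infection, "a fold increase will be applied to call a subject seropositive to G and/or N ELISA (or F in case of placebo subjects"), that is, G and/or N in either arm and F in placebo subjects only. No fold value is stated.

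**Analysis in the protocol.** Section 11.6 reads: "Incidence of any RSV infection, as described in Section 3.2, in Ad26.RSV.preF and placebo subjects will be summarized by descriptive statistics". Section 3.2 has two categories. Suspected infection is a defined combination of persistent symptoms. Confirmed infection is a "subject with suspected RSV infection and positive for RSV on the basis of RT-PCR conducted centrally".

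**Analysis in the SAP.** Section 7 uses the same two categories, split by severity, but its opening clause limits the summary to the situation in which Cohort 1 has a severe LRTI. SAP 1.6, which records changes to the planned analyses, covers only the interim analyses and what the data monitoring committee receives.

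**Other mentions of serology.** Protocol 9.2.1 and 9.2.2 allow serological testing as an option. Section 11.3.1.2 lets the clinical endpoint committee judge RSV positivity from all available information when RT-PCR is missing.

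**The concern.** Two things do not line up. First, the protocol promises an infection summary in every case, while the SAP, which is the document the programmers will follow, promises one only after an event that may well not happen. The Amendment 4 rationale itself describes seropositive toddlers as having little or no risk of severe RSV disease. If the SAP is followed literally, a stated objective could go unreported even though the symptoms and swabs have been collected.

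Second, the endpoint reaches further than its analysis. A child with no symptoms, or with serological evidence only, fits neither category in Section 3.2 or SAP 7. If serology is run, the plan does not say how the results enter the infection rate. The endpoint wording would then be the only guide, and it allows an antigen in placebo that cannot be used in vaccinees.

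**Working it through.** The documents give no figure for this endpoint, so there is none to reproduce. The only related figures are in the Protocol 11.2 table, which uses 1 − (1 − p)^N. One cell as a check: N = 24 and p = 1% gives 1 − 0.99^24 = 21.4%, and the table prints 21%.

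**Step 1. Does the analysis cover the endpoint?**

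- Symptomatic, RT-PCR positive: in the endpoint; covered by 11.6; covered by SAP 7 only if a severe LRTI occurs.
- Symptomatic, RT-PCR missing, positive by serology: in the endpoint; under 11.6 and SAP 7 it can count only as suspected. Committee adjudication under 11.3.1.2 may settle the individual case, but it is not a by-arm summary.
- Asymptomatic, positive by fold rise: in the endpoint; in no category of 11.6 or SAP 7.

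**Step 2. How likely is it that SAP 7 yields no summary?** The input is 36 toddlers (Protocol 3.1 and Table 5: 24 active, 12 placebo; SAP 1.2 text also says 36, although SAP Table 1 still shows 32 and 16). The per-child risk r of a severe LRTI is an assumption. The values 0.5%, 1% and 2.5% are used; they also appear as generic adverse-event rates in the 11.2 table. With independent children, P(no event) = (1 − r)^36:

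- r = 0.5%: 0.995^36 = 0.835, about 83%
- r = 1%: 0.99^36 = 0.696, about 70%
- r = 2.5%: 0.975^36 = 0.402, about 40%

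Protocol 3.4.4 also quotes 2.5%, for severe-LRTI hospitalisation in the control group of a 1960s formalin-inactivated vaccine study. That is a different population and a different event, so it does not support r here. The Amendment 4 remark concerns severe RSV disease. The SAP 7 trigger, as worded, is a severe LRTI, and the criteria in 11.3.1.1 do not require RSV. The remark therefore points to a low r without fixing it.

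**Step 3. What would the F clause do if serology were compared by arm?** The Introduction says the vaccine carries a "transgene that encodes for the pre-fusion conformation-stabilized F protein (pre-F) derived from the RSV A2 strain", so an F rise cannot separate infection from vaccination in the active arm. If F is additional to G and/or N, one F-only call adds 1/12 = 8.3 percentage points to the placebo rate, and no such call can be made among the 24 vaccinees. How many such calls would occur cannot be derived from the documents.

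**The case against.** **The SAP 7 condition may be meant only for the severity split.** The split is empty without a severe case, 11.6 remains unconditional, and tables are specified in a separate data presentation document that is not available here. A summary may therefore be produced anyway. That is possible, and it is why the point is put as what the SAP specifies, not as what will happen. But the sentence conditions the whole summary, not just the split, and nothing in SAP 1.6 or elsewhere corrects it.

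**Serology is not wholly unhandled.** It is optional, and the endpoint committee can use it when RT-PCR is missing. Both statements are true. Neither produces a by-arm summary of serological or asymptomatic infection.

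**The endpoint is exploratory.** No hypothesis is tested, and only 12 children receive placebo. This stands and limits the severity. The feasibility note in the Synopsis and 11.3.1 does not help, because it covers severe RSV-LRTI and medically attended RTI, not infection as such.

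**Stronger readings that the text does not support.** A reader might infer that the placebo-only F clause biases the planned comparison in favour of the vaccine. No passage plans a by-arm serological analysis, and the rate under 11.6 contains no serological call, so the planned summary carries no such bias. The asymmetry would matter only if serology were later tabulated by arm under the endpoint wording with F counted.

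A reader might also infer that F-only rises will remove placebo samples from the per-protocol immunogenicity set, since Protocol 11.1 and SAP 2.3.2.1 exclude samples after infection shown by RT-PCR or by other, unnamed sources. The documents do not say whether an F-only rise counts. Either ruling has a cost: excluding such samples makes exclusion depend on a measured outcome, and keeping them may leave naturally infected placebo samples in the summaries. The planned full-analysis-set tables limit the issue, so no change is proposed there.

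**Conclusion.** The point holds in two parts. The firm part is a conflict between documents: SAP 7 makes the infection summary conditional, Protocol 11.6 and the objective do not, and SAP 1.6 does not record the difference. At assumed severe-LRTI risks of 1% or below, SAP 7 as written would more likely than not specify no infection summary (about 70% at 1%, 83% at 0.5%). At 2.5% the chance is about 40%. These figures rest on assumed risks, 36 children and independence between children.

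The second part is a gap: the serological and asymptomatic component of the endpoint has no by-arm analysis. Its practical weight depends on whether serology is run at all. The 8.3 points per F-only call is a conditional figure, not an estimate of bias in the planned analysis. Severity is low to moderate.

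**What to change.** Make both changes in the SAP.

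1. In Section 7, delete the severe-LRTI condition. Tabulate suspected and RT-PCR-confirmed infection by arm in all cases, and add the severe/non-severe split if a severe case occurs.
2. If serology is run, also tabulate serological infection by arm with the same G and/or N rule in both arms, stating the fold rise and the sample pair. List F-only rises in placebo separately as supportive information that does not enter the compared rate. Record this treatment of F in SAP 1.6.

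The cost is wording and the matching table specifications. No visit or sample is added, and Protocol Section 11 already leaves analysis detail to the SAP. The downside is that placebo infections visible only through F do not count toward the compared rate.
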